#### 16.13 Accrual Rate and Study Duration

Given previous data from Mayo, it is estimated that this study will accrue 2-3 patients per month. Each cohort of 3 will require approximately 2.5 months (1.5 months for accrual and treatment, and an additional month data maturity and evaluation) to assess. Therefore, the overall study duration (including enrolling, treatment and evaluation) will range approximately from minimum of 5 months (when only 2 cohorts are required) to a maximum of 10 months (when 4 cohorts of 3 are required) for the dose escalation (Phase I) portion of the trial. The additional patients at the MTD will require approximately 16 months to accrue and an additional 4 months to assess. This means the study will take somewhere between 25 months and 30 months.

### 16.2 Phase I Study Design

The primary endpoint of the phase I portion of this trial is to estimate the MTD of anetumab ravtansine combined with atezolizumab. A standard 3+3 phase I design will be utilized. Three patients will be treated at each dose level and observed for a minimum of three weeks (i.e. one full cycle) before new patients are treated. Doses will not be escalated in any individual patient.

#### 16.21 MTD Definition

MTD is defined as the dose level below the lowest dose that induces dose-limiting toxicity (DLT) in at least one-third of patients (at least 2 of a maximum of 6 new patients). A total of 6 patients treated at the MTD will be sufficient to

identify common toxicities at the MTD. For instance, those toxicities with an incidence of at least 25% will be observed with a probability of at least 82% ( $1 - (1 - 0.25)^6$ ). Refer to Section 7.6 for definition of dose-limiting toxicity (DLT).

- 16.22 MTD Determination:  
Dose Escalation: The phase I portion of this study will utilize a standard cohort of three design. The first cohort of three patients will be treated at dose level 1. Decisions on when and how to dose escalate are described below.
- 16.23 The first cohort of three patients will be treated at the starting dose level 1.
- 16.24 Three patients will be treated at a given dose level combination and observed for at least 21 days from start of treatment to assess toxicity.
- 16.25 If DLT is not seen in any of the 3 patients, 3 new patients will be accrued and treated at the next higher dose level. If DLT is seen in 2 or 3 of 3 patients treated at a given dose level, then the next 3 patients will be treated at the next lower dose level, if only 3 patients were enrolled and treated at this lower level.
- 16.26 If DLT is seen in 1 of 3 patients treated at a given dose level, up to 3 additional will be enrolled and treated at the same dose level. If DLT is seen in at least one of these additional three patients ( $\geq 2$  of 6), the MTD will have been exceeded, and further accrual will cease to this cohort (see 16.113 for further details). If dose-limiting toxicity (DLT) is not seen in any of the three additional patients, 3 new patients will be accrued and treated at the next higher dose level.
- 16.27 After enrolling 6 patients on a specific dose level, if DLT is observed in at least 2 of 6 patients, then the MTD will have been exceeded and defined as the previous dose unless only 3 patients were treated at the lower dose level. In that case, 3 additional patients will be treated at this lower dose level such that a total of 6 patients are treated at the MTD to more fully assess the toxicities associated with the MTD.
- 16.28 Dose de-escalation: If DLT meets the stopping boundaries set by the above dose escalation algorithm at dose level 1 (for example, more than 1 out of 3 patients or more than 1 out of 6 patients), the next cohort of three patients will be entered at a dose level of -1. Further dose re-escalation will depend on the toxicity profile observed at dose level -1, and re-evaluation of the regimen by the study team may be done.
- 16.29a If a patient fails to complete the initial course of therapy (defined as drug administration and 21 days) for reasons other than DLT defined adverse events, the patient will be regarded as uninformative in regard to the primary study goal and an additional patient will be treated at the current dose level; however, all toxicity information will be utilized in the analysis.
- 16.29b Operating Characteristics for Phase I portion of trial

The following table gives the probability of dose escalation at a single dose level as a function of the true probability of DLT at that level using the Cohort 3+3 design described in section 16.2.

| True Rate of DLT (%) | Probability of Dose Escalation |
|----------------------|--------------------------------|
| 10                   | 0.91                           |
| 20                   | 0.71                           |

|    |      |
|----|------|
| 30 | 0.49 |
| 40 | 0.31 |
| 50 | 0.17 |

### 16.3 Analysis Plans for Phase I portion:

All the relevant results pertaining to toxicity, MTD, response, and timed endpoints will be examined in an exploratory and hypothesis-generating fashion. The small sample size and the heterogeneous patient population associated with phase I studies restricts the generalizability of the results. Any notable statistical result should only be viewed as preliminary evidence for further study in Phase II trials rather than a definitive finding in and of itself. All results will be shown overall and by dose level.

#### 16.31 Adverse Events Profile

The number and severity of all adverse events (overall and by dose-level) will be tabulated and summarized in this patient population. The Grade 3+ adverse events will also be described and summarized in a similar fashion. This will provide an indication of the level of tolerance for this treatment combination in this patient group.

#### 16.32 Toxicity Profile

The term toxicity is defined as adverse events that are classified as either possibly, probably, or definitely related to study treatment. Non-hematologic toxicities will be evaluated via the ordinal CTC standard toxicity grading. Hematologic toxicity measures of thrombocytopenia, neutropenia, and leukopenia will be assessed using continuous variables as the outcome measures (primarily nadir) as well as categorization via CTC standard toxicity grading. Overall toxicity incidence as well as toxicity profiles by dose level, patient and tumor site will be explored and summarized. Frequency distributions, graphical techniques and other descriptive measures will form the basis of these analyses.

#### 16.33 To identify preliminary evidence of clinical activity (i.e. confirmed response, timed endpoints, etc.). A confirmed response is defined to be a CR or PR noted as the objective status on two consecutive evaluations at least 4 weeks apart. Confirmed response will be evaluated using the first 6 months of treatment. All patients meeting the eligibility criteria who have signed a consent form and have begun treatment will be evaluable for response. Responses will be summarized by simple descriptive summary statistics delineating complete and partial responses as well as stable and progressive disease in this patient population.

The data on time-related variables will be summarized descriptively. These include time until any treatment related toxicity, time until treatment related grade 3+ toxicity, time until hematologic nadirs (ANC, platelets, hemoglobin), time to progression and time to treatment failure, where time to treatment failure is defined as the time from registration to documentation of progression, unacceptable toxicity, or refusal to continue participation by the patient.

Other clinical activity endpoints will also be explored, including overall survival, progression-free survival, etc. overall and by dose level. These endpoints will be more fully explored during the Phase II portion of the

study.

#### 16.4 Phase II Statistical Design

- 16.41 Interim Analysis: In the expanded cohort part of the trial, 17 patients will be accrued (this will include the patients treated at the MTD from the phase I component). If 3 confirmed responses or less are observed in the first 17 eligible patients, then the trial will be terminated and the treatment deemed not worthy of further study. If at least 4 confirmed responses are observed among these 17 patients, then an additional 20 patients will be accrued to the second stage.
- 16.42 Final Analysis: If 11 or more confirmed responses are observed at the end of the trial in the first 37 eligible patients, the treatment will be considered promising. This design yields at least 90% probability of a positive result if the true response rate is at least 40%.
- 16.43 Over Accrual: If more than the target number of patients are accrued, the additional patients will not be used to evaluate the final decision rule or used in any decision making process. Analyses involving over accrued patients are discussed in Section 16.54.
- 16.44 Other considerations: Adverse events, quality/duration of response, and patterns of treatment failure observed in this study, as well as scientific discoveries or changes in standard care will be taken into account in any decision to terminate the study

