#### 3.2 Registration - Inclusion Criteria

- 3.21 **Phase I only:** Diagnosis of advanced/metastatic NSCLC for which no standard treatment option. **Phase II only:** Advanced NSCLC patients who have received at least 1 platinum-based systemic chemotherapy regimen
- 3.22 Patients with tumors having actionable genomic alterations should have received prior therapy with FDA approved agents targeting these alterations (ie EGFR, ALK, ROS1, BRAF V600E)
- 3.23 ECOG performance status 0 or 1. (See Appendix A)
- 3.24 **Phase II only:** Must have at least one measurable lesion as defined by RECIST criteria (see Section 11).
- 3.25 Ability to understand and the willingness to sign a written informed consent document.
- 3.26 Histological or cytologically confirmed NSCLC that shows moderate or stronger mesothelin expression in 30% of tumor cells by a companion assay. MSLN expression score using Ventana IHC SP74 assay. Phase I only: In addition 5-30% tumor cells and 1, 2, or 3+ MSLN score. Phase II only: 30% tumor cells and either 2+/3+.
- 3.27 Life expectancy of  $\geq 12$  weeks.
- 3.27 Adequate bone marrow and organ function as defined by the following laboratory values  $\leq 14$  days prior to registration:
  - Absolute neutrophil count  $\geq 1.5 \times 10^9/L$
  - Platelets  $\geq 100 \times 10^9/L$
  - Hemoglobin  $\geq 9$  g/dL
  - Chemistries as follows:
    - Potassium  $\geq$  lower limit of normal (LLN) range for the institution
    - Calcium  $\geq$  LLN (corrected for serum albumin, if albumin abnormal)
    - Magnesium  $\geq$  LLN
    - Sodium  $\geq$  LLN
    - Phosphorus  $\geq$  LLN.
 NOTE: Supplementation may be given before the first dose of study medication.
  - INR  $\leq 1.5$

- Serum creatinine  $\leq 1.5$  mg/dL or creatinine clearance  $\geq 50$  mL/min (calculated by Cockcroft Gault equation)

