#### 13.7 Ineligible

A patient is deemed *ineligible* if after registration, it is determined that at the time of registration, the patient did not satisfy each and every eligibility criteria for study entry. The patient may continue treatment off-protocol at the discretion of the physician as long as there are no safety concerns, and the patient was properly registered. The patient will go directly to the event-monitoring phase of the study (or off study, if applicable).

- If the patient received treatment, all data up until the point of confirmation of ineligibility must be submitted. Event monitoring will be required per Section 4.0 of the protocol.
- If the patient never received treatment, on-study material must be submitted. Event monitoring will be required per Section 4.0 of the protocol.

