##### 16.51 Primary Outcome Analyses:

- 16.511 Definition: The primary endpoint of this trial is the proportion of patients who achieve a confirmed response. A confirmed response is defined as PR or CR noted as the objective status on two consecutive evaluations at least 4 weeks apart. All patients meeting the eligibility criteria who have signed a consent form and have begun treatment will be evaluable for response, unless they are determined to be a major violation.
- 16.512 Estimation: The proportion of successes will be estimated by the number of successes divided by the total number of evaluable patients. Exact binomial 95% confidence intervals for the true success proportion will be calculated.

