### 17.3 Mesothelin tissue analysis

Preclinical and Phase I evidence suggests that mesothelin expression (or expression level above a certain threshold) in human tumors may be required for binding, internalization, and anti-tumor activity of anetumab ravtansine. Mesothelin expression will be prospectively evaluated for patient selection. All patients will provide formalin-fixed, paraffin-embedded (FFPE) tumor samples or fresh tissue to analyze mesothelin expression as a potential predictive biomarker. If archival material is not available a fresh biopsy can be taken, if the investigator deems the procedure to be safe for the patient. Patients will be stratified to the appropriate cohort based on the following criteria: High mesothelin expression of  $\geq 30\%$  of viable tumor cells with 2+ or 3+ membrane staining intensity will be in the “mesothelin high” group. Low-mid mesothelin expression of at least 5% viable tumor cells positive for MSLN expression (all intensities) but  $< 30\%$  2+ or 3+ membrane staining will be in the “mesothelin low” group. The IHC test used to detect mesothelin expression (Ventana MSLN [SP74] IHC assay) is currently investigational and not approved by FDA or other regulatory authorities. Both groups will be enrolled in the phase I dose escalation portion but only the “mesothelin high” group will be enrolled in the phase II expansion portion of the study.

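### Phase I patients at the MTD fill Phase II places without having to meet the Phase II mesothelin and measurable-disease criteria, so the stated 90% power is not assured for the population Phase II enrols

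*Combined protocol and SAP*

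**What the plan says.** The stage 1 rule in 16.41 states that "17 patients will be accrued (this will include the patients treated at the MTD from the phase I component"). It continues: "If 3 confirmed responses or less are observed in the first 17 eligible patients, then the trial will be terminated". Four or more responses lead to 20 further patients, and 16.42 calls the treatment promising at 11 or more confirmed responses in 37. Section 16.12 breaks the 37 into 6 patients from Phase I and 31 from Phase II. The synopsis also counts the Phase I patients treated at the MTD. None of these places adds a condition on who may be carried over.

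The entry criteria differ by phase:

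- **Mesothelin (3.26).** "Phase I only: In addition 5-30% tumor cells and 1, 2, or 3+ MSLN score". Phase II requires 30% of tumour cells at 2+ or 3+. Section 17.3 confirms the split: "Both groups will be enrolled in the phase I dose escalation portion but only the" mesothelin-high group goes into the Phase II expansion.
- **Measurable disease (3.24).** "Must have at least one measurable lesion as defined by RECIST criteria" is labelled as applying to Phase II only.
- **Prior treatment (3.21).** Phase I takes patients with no standard option left. Phase II takes patients who have had at least one platinum-based regimen.

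The evaluable set is defined in 16.511: "All patients meeting the eligibility criteria who have signed a consent form and have begun treatment will be evaluable for response", unless there is a major violation. Section 13.7 calls a patient ineligible if, at registration, "the patient did not satisfy each and every eligibility criteria for study entry".

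**The concern.** A mesothelin-low Phase I patient, or one without a measurable lesion, satisfies the criteria under which he or she entered the study. Under 13.7 that patient is not ineligible, and under 16.12 he or she is one of the six carried over. So up to 6 of the 17 stage 1 patients (6/17 = 35%) and 6 of the final 37 (6/37 = 16%) could be patients whom Phase II itself would turn away.

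The protocol gives two reasons to expect fewer responses in them. Section 17.3 says that "mesothelin expression (or expression level above a certain threshold) in human tumors may be required for binding, internalization, and anti-tumor activity of anetumab ravtansine", and 1.22 reports objective responses only where mesothelin expression was strong. Also, partial response in 11.432 is a 30% fall in the sum of target-lesion dimensions. A patient without a target lesion cannot reach it and could count only through disappearance of non-target disease (11.433).

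What is at stake is a rule that ends the trial. If the carried-over patients respond less often, an active regimen is more likely to be stopped at 17, the power claim in 16.42 does not hold for the Phase II population, and the reported response rate mixes two populations.

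**Working it through.** **Inputs from the documents.** Null and target response rates 20% and 40%, with both error rates set at 0.10 (synopsis). Stop at 3 or fewer of 17; promising at 11 or more of 37 (16.41, 16.42). Carry-over of 6 (16.12).

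**Assumptions, not in the documents.** Let k be the number of counted Phase I patients who do not meet the Phase II criteria, and q their response rate. I take k = 1, 3 and 6, and q from 0 to 30%. All other counted patients respond at rate p.

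**Step 1: reproduce the plan.** With one common rate p,

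P(promising) = Σ over x = 4 to 17 of P(X₁ = x) · P(X₂ ≥ 11 − x), where X₁ ~ Bin(17, p) and X₂ ~ Bin(20, p).

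| p | P(stop at stage 1) | P(promising) |
|---|---|---|
| 0.20 | 0.549 | 0.0948 (type I error) |
| 0.40 | 0.046 | 0.9033 (power) |

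The stated 90% holds, with 0.9033 − 0.90 = 0.0033 to spare.

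**Step 2: let k of the first 17 respond at q.** X₁ becomes the sum of Bin(17 − k, 0.40) and Bin(k, q). Stage 2 is unchanged, because the carried-over patients all sit in the first 17.

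One cell by hand, k = 6 and q = 0: stage 1 rests on the other 11 patients, so P(stop) = P(Bin(11, 0.40) ≤ 3) = 0.296, against P(Bin(17, 0.40) ≤ 3) = 0.046 as designed.

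Power, with the probability of a false stop at stage 1 in brackets:

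| k | q = 0 | q = 10% | q = 20% | q = 30% |
|---|---|---|---|---|
| 1 | 0.875 (0.065) | 0.882 (0.060) | 0.889 (0.056) | 0.896 (0.051) |
| 3 | 0.798 (0.124) | 0.828 (0.101) | 0.856 (0.080) | 0.881 (0.062) |
| 6 | 0.608 (0.296) | 0.709 (0.203) | 0.791 (0.132) | 0.855 (0.081) |

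Every cell is below 0.90. With k = 0, or with q = 40%, the design values return.

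**Step 3: rate needed to keep 90% power.** Solving for the rate in the Phase II-eligible patients, from q = 0 to q = 30%: 41.2% to 40.2% for k = 1, 44.5% to 41.0% for k = 3, and 51.9% to 42.6% for k = 6.

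**Step 4: type I error.** With the other patients at 20% and k = 6, it is 0.022, 0.052, 0.095 and 0.149 at q = 0, 10%, 20% and 30%. It exceeds the design value only if the carried-over patients respond better than the null rate.

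**The case against.** The best defence is that *eligible* already means Phase II-eligible. Sections 16.41 and 16.42 sit under the Phase II design, section 3.2 labels its criteria by phase, and 17.3 keeps the expansion for mesothelin-high tumours. Section 16.33, in the Phase I plan, uses nearly the same sentence on evaluability as 16.511, so each could be read as meaning its own phase's criteria. That reading is possible, but no text states it. Section 13.7 points to study entry, and 16.12 counts all six without condition. Two readings remain, and they can give different counts for a stopping rule.

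The size of the loss can also be challenged, and here part of the objection stands. The power statement is correct for a single common rate. The low end (k = 6, q = 0) requires all six to fall outside the criteria and none to respond. Mesothelin-low patients still receive atezolizumab, whose mechanism does not depend on mesothelin, and the evidence in 1.22 is single-agent and mainly from other tumours. At q of 20 to 30%, the loss is 0.7 to 1.4 points for k = 1 and 2.2 to 4.7 points for k = 3. The likely error is also a missed active regimen rather than a false claim.

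Finally, 3.21 makes Phase I narrower in one respect, so matching the criteria does not guarantee a common response rate. That is true. It limits what the fix can achieve but does not remove the need for it.

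**Conclusion.** The concern holds. As written, the plan lets patients outside the Phase II criteria count toward the 17 and the 37, and the 0.3-point margin means that a single such patient responding at 30% or less takes power below the stated 90%. With three such patients power is 0.798 to 0.881; with six it is 0.608 to 0.855.

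These figures rest on assumed values of k and q and on a 40% rate in everyone else. The direction is supported by the protocol's own text but is not established for the combination in NSCLC, and the Phase II goal, which says only MSLN+, does not settle which patients belong in the estimate. The supported conclusion is therefore that the 90% is not assured, not that it is wrong. Type I error is not a concern unless the carried-over patients respond at more than 20%. The gap should be fixed because it affects a trial-ending rule and costs little to close.

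**What to change.** In 16.12, 16.41, 16.42, 16.511 and the synopsis, state that a Phase I patient counts toward the 17, the 37 and the response denominator only if treated at the recommended dose and meeting the Phase II versions of 3.24, 3.26 and 3.21. Define *eligible* in those terms. Include 3.21 because it also differs by phase. Report the other Phase I patients in the Phase I summary only, and fill their places with Phase II registrations. If only these patients count and they share one rate, the design figures apply again: power 0.903 and type I error 0.095.

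The cost is a wording amendment and k further registrations, at most 6, or 6/3 = 2 to 6/2 = 3 months at the accrual of 2 to 3 per month in 16.13.

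Restate the accrual ceiling at the same time, because the two accounts of 49 differ. The synopsis implies 12 + 37 = 49, with no overlap and no replacements. Section 16.12 gives 43 evaluable + 6 replacements = 49, with 6 patients overlapping. Refilling all six places fits within 12 + 37 = 49 but leaves no room for replacements, which 13.6 requires for inevaluable Phase I patients. With k places refilled and the 6 replacements kept, the ceiling is 43 + k + 6 = 49 + k, which is at most 55.

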#### 16.5 Analysis Plan for Phase II portion of trial

The analysis for this trial will commence at planned time points (see 16.3) and at the time the patients have become evaluable for the primary endpoint. The Statistician and Study Chair will make the decision, in accord with CCS Standard Operating Procedures, availability of data for secondary endpoints (e.g., laboratory correlates), and the level of data maturity. It is anticipated that the earliest date in which the results will be made available via manuscript, abstract, or presentation format is when last patient has been followed for at least 6 months.

##### 16.51 Primary Outcome Analyses:

- 16.511 Definition: The primary endpoint of this trial is the proportion of patients who achieve a confirmed response. A confirmed response is defined as PR or CR noted as the objective status on two consecutive evaluations at least 4 weeks apart. All patients meeting the eligibility criteria who have signed a consent form and have begun treatment will be evaluable for response, unless they are determined to be a major violation.
- 16.512 Estimation: The proportion of successes will be estimated by the number of successes divided by the total number of evaluable patients. Exact binomial 95% confidence intervals for the true success proportion will be calculated.

